## **5.5 Study Evaluations**

### **5.5.A. Summative Evaluation of Implementation**

We will conduct a summative evaluation of EPIC implementation after completing study Phase 2. We will characterize successful implementation along three (dependent) variables related to elements of the RE-AIM framework (reach, adoption, and implementation). The aims of Phase 2 will address the remaining two elements of RE-AIM (effectiveness and maintenance). We will evaluate RE-AIM along the measurement model described in Table 5 below.

**5.5.A.i. RE-AIM Measures for the Summative Evaluation.** We will assess reach by comparing the characteristics of enrolled study participants to those of all eligible patients participating. We will evaluate adoption among PACTs at the facility level by evaluating PACT team-level characteristics that differ among those with members who agree to participate versus others in a given facility. We will also calculate the total number of personalized goal-setting sessions that occur following a scheduled EPIC group session divided by the total number of EPIC group sessions patient-participants attended. Finally, we will collect descriptive information about adoption such as frequency and percentage of different types of professional disciplines of PACT members who participate in the personalized goal-setting. For implementation, we will evaluate the proportion of group sessions attended per patient, with the total possible number of group sessions (i.e., six) as the denominator and the proportion of individual sessions attended per patient (i.e., 0-6) as the numerator. We will also examine fidelity ratings of all VA staff

**Table 5. RE-AIM Elements and Corresponding Measures**

RE-AIM Elements (Phase 2)	Proposal's Corresponding Measures
Reach: Representativeness of patients who are willing to participate in the intervention	Characteristics of enrolled study participants from a given PACT patient panel compared to those of all PACT patients meeting eligibility criteria from that panel
Effectiveness: Intervention's impact on important outcomes, including negative effects like diabetes distress	Differences in HbA1c and DDS between EPIC and EUC study arms at 4 months (post-intervention)
Adoption: Representativeness of settings & intervention agents willing to initiate a program and their actual use of program or intervention components	
 
1) Characteristics of PACT teams with participating members
 
2) Timing and frequency of one-on-one sessions following each group sessions
 

Implementation: The intervention agents' fidelity to the various elements of an intervention's protocol; patients' use of the intervention strategies; and the costs and cost-effectiveness of the intervention	
 
1) Proportion of group sessions attended (out of six) for each enrolled patient
 
2) Proportion of individual sessions attended (out of six) for each enrolled patient
 
3) Objective ratings of individual session providers' fidelity to the collaborative goal-setting methodology using a structured fidelity rating process completed by a behavioral coaching expert on the study team
 
4) Patients' perceptions of goal-setting engagement by providers in both the intervention and EUC arms
 
5) Objective ratings of goal and action plan quality using our validated GET-D tool by trained research staff blinded to random assignment
 
6) Cost-utilization and cost-effectiveness of EPIC compared with EUC arms.
 

Maintenance: Long-term effects of a program on outcomes 6 or more months after the most recent intervention contact	Differences in HbA1c and DDS between EPIC and EUC study arms to measure intervention persistence at 10 months

trained to lead the EPIC group sessions and those trained as individual session providers, who conduct personalized, collaborative goal-setting; these ratings will be performed after training by a behavioral coaching expert on the study team. The study team will then measure patient-participants' self-reported ratings of how much their group leader and individual session provider(s) engaged them in goal-setting using a validated measure, and objective ratings of goal and action plan quality using our previously validated rating GET-D tool. We will assess cost-effectiveness of this study from a perspective of the VA health care system using a

comprehensive cost-based database system. We will use a micro-costing approach to track and record all expenses related to the EPIC and EUC components and non-research related resource consumptions such as the educational materials and staff time spent on both study arms. We will retrieve medical utilization and cost data from the National Patient Care Database and the Decision Support System. We have experience working with each of these data sources in our prior HSR&D funded work. The National Patient Care Database includes outpatient and inpatient clinical, demographic, and utilization data (e.g., patient age, race, diagnosis and procedure codes, clinic location where care is provided, and the provider of care). The Decision Support System, a managerial cost accounting system, produces National Data Extracts that provide cost and utilization information for a range of health care activities, including laboratory, pharmacy, radiology, outpatient services, and inpatient treating specialty units. Unit cost of personnel time will be based upon the actual salary rate and fringe. Unit cost of other resources such as supplies and facilities will be derived from the VA accounting system. Total costs for each patient will be the summed products of quantities of resources used multiplied by the unit cost for those resources. All costs will be adjusted to constant US dollars in 2016. For cost-effectiveness, we will use two measures: 1) number of study patients with clinically significant improvements in HbA1c; and 2) number of quality adjusted life-years using the validated EQ-5D instrument to derive health utility weights. The utility score (weight) of each individual patient at each observational interval over the trial period (baseline to 4 months to 10 months) will be calculated according to the scoring algorithms provided by the EQ-5D developers. The primary end-point measures of cost-effectiveness are: 1) the incremental cost per additional number of study patients whose HbA1C are significantly improved and 2) the incremental cost per additional quality adjusted life-year gained, of the intervention relative to the control group.

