### 5.1.J. Potential Risks

The potential risks of harm to study participants are low for all phases of this study. In Phase 1, the key informant interviews solicited information on how best a) to adapt EPIC to include point-of-care information on patient activation and functional health literacy; and b) to integrate the intervention into routine work flows. The primary risk to clinician and staff participants was loss of time and potential breach of confidentiality.

The risks for staff participating in Phase 2 of the study are also considered minimal for this project because diabetes care is part of their regular clinical duties. There is a small possibility for loss of confidentiality, although participants will be assigned unique, study ID#s, and all analyses will be blinded.

For patient-participants in Phase 2, this trial poses minimal risk; however, there are still some potential risks associated with the proposed tests to assess the impact of the intervention, as well as the intervention itself. Risks associated with the assessments are low given that the items assessed are normal daily activities including blood draws that are conducted as part of the standard of care. There is also a small risk for breach of confidentiality, but patient-participants will also be assigned unique, study ID#s for analysis and all results will be reported in aggregate. With our eligibility criteria and multi-gated recruitment approach, we should be able to effectively screen-out any individuals for whom this intervention is contraindicated. However, because this intervention aims to improve patients' management of their health through assisting in the implementation of self-management changes, a small risk remains that some patients may experience hypoglycemia after successfully making these modifications. We will closely monitor these potential symptoms and have developed a protocol for interceding whenever hypoglycemia symptoms manifest. We have successfully utilized this protocol in prior studies.

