**5.2.B. Patients' eligibility criteria.** Inclusion criteria: Using the Corporate Data Warehouse, we will identify active patients at participating facilities meeting the study inclusion criteria: 1) ICD-9-CM codes indicating diabetes, and 2) average HbA1c level  $\geq$  8% in the prior 6 months. We will not use preparatory to research data. We will conduct a data search under approved waivers to identify eligible patients. Exclusion criteria: We will use a medical record review to exclude potential participants with the following clinical conditions that would render participation in a group clinic inappropriate: 1) metastatic cancer or receiving hospice care, 2) limited life expectancy (as identified using a validated algorithm developed in our prior work [see Attachment 1]), 3) clinician recommendations to not titrate therapy due to prior history of significant hypoglycemic events, 4) age <18 years, 5) active bipolar or psychotic disorder, 6) documented active substance abuse, or 7) documented dementia. We estimate that 20% of records will be excluded at chart review, resulting in approximately 3,020 letters sent to Veterans. We will exclude participants at the time of screening who report to study staff that they 8) have substantial hearing or vision loss, such that participation with the materials and group exercises would not be possible, 9) cannot attend bi-weekly group clinic sessions due to transportation or availability barriers, 10) have significant cognitive impairment (three or more errors on an established six-item screening exam), 11) have active substance-abuse disorders, or 12) are not comfortable discussing their health and health care in a peer-group setting.

Patients will be secondarily excluded if their HbA1C level falls below 7.5% at baseline. Patients whose baseline levels fall below 7.5% may have limited ability for meaningful HbA1c change without significant concerns for hypoglycemia.

We will notify all participants identified as having uncontrolled diabetes but who do not meet the final eligibility criteria (i.e., whose HbA1c drops below 7.5% at baseline) of their results. A note will be placed in their medical record indicating this finding and they will be withdrawn from the research.

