#### **5.5.B. Data Collection Strategy § 5.1.H.**

#### **5.5.C. Study Variables § 5.1.I.**

### **5.6 Data Analysis**

#### **5.6.A. Sample Size Calculation/Sample size determination**

Sample size is calculated according to the estimated intervention effect size at post-intervention. We then estimate power to detect treatment effects at the post-maintenance (10-month) follow-up as well as power to detect treatment differences in linear change across the three time points for a 3-level cluster-randomized trial with repeated assessments. We will adjust models for baseline covariates of study patients. All tests will be two-sided with an alpha of 0.05. In our recent RCT, differences in HbA1c change between EPIC versus enhanced group education indicated medium treatment effects at post-treatment and at 1-year (Cohen's  $d = 0.48$  and  $0.42$ , respectively). A similar trial revealed a treatment difference between a glucose self-monitoring protocol and an active control group in DDS scores that correspond to large effects of treatment at 1-year (all pre-post  $d$ s  $> 0.80$ ). To capture treatment effects for both clinical and patient centered outcomes in this implementation trial, a conservative small-to-medium effect size of  $d = 0.40$  (which is 16.67% smaller than the effect found for HbA1c in the prior trial) was used to calculate sample size. Assuming no intra-class correlation (ICC) within

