PACTs, 100 patients in each treatment arm (i.e., EPIC and EUC) will allow for 80% power to detect small-to-medium effects and 98% power to detect medium effects ( $d = 0.50$ ). To account for the dependency among patients within a PACT, the Design Effect (Deff) was applied, following the approach of Schnurr et al. The sample size was inflated using the formula,  $Deff = 1 + (n-1)\rho$ , where  $n$  is the average number of patients per PACT and  $\rho$  is the ICC for PACTs. In our preliminary work, we identified an ICC for PACTs of 0.0183, an average of 27 eligible patients per PACT, and expect that an average of 12 patients per PACT will participate, which yields  $Deff = 1 + (12-1) * 0.0183 = 1.2013$ . Applying this adjustment, the minimum number of patients in the clustered design is  $100 \times 1.2013 = 120$  in each treatment group. Further adjusting for a maximum of 15% attrition, 142 patients will be recruited for each treatment group (total  $N = 284$ ). Therefore, the minimum number of PACTs to be sampled for this nested analysis is technically 11.8, (i.e.,  $142/12$ ), which will be rounded up to 24 PACTS. This is highly feasible, representing just 32.5% of the total number of PACTs (75) at all study sites. Treatment group effect sizes as small as  $d = .40$  can be detected with 80% power at 1-year given a total of 284 patients (an average of approximately 12 patients randomized to either EPIC or EUC from within 24 PACTs sampled), even after accounting for maximum attrition and estimated dependency within PACTs. A sample size of 284 participants is adequate for repeated measures analyses as well. Optimal design software estimated power to detect treatment group differences in linear change across all three assessments. Prior data indicated a main effect of treatment (EPIC versus enhanced group education) for linear change in HbA1c of 0.20, and between – and within – PACT variance in linear change of 0.018 and 0.206, respectively. These values indicate a small-to-medium between-groups effect size of 0.42. A total of 284 participants allows for 80% power to detect a slightly larger effect size ( $\delta = .53$ ) for repeated measures analyses of linear change over time. Furthermore, there is 98% power to detect a medium effect size of  $\delta = .75$ .

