Specific Aim 2: The distributional nature of all variables will be assessed, and nonparametric tests (e.g., Fisher's Exact Test; Mann-Whitney test), data transformations (e.g., log linear), or other alternate methods (e.g., weighted least squares regressions) will be conducted where appropriate. First, we will compare baseline demographic, clinical, and patient-centered variables (including medication use) between EPIC and EUC with chi-square and independent samples t-tests. Variables with p-values  $< 0.25$  will be included as control variables or propensity scores in subsequent models. We will then compare baseline demographic, clinical, and patient-centered variables between those who complete the study and those who do not using chi-square and independent samples t-tests. Outcome analyses at both post-intervention and post-maintenance will be intention-to-treat and will use the multiple imputation procedures Proc MI and MINANALYZE in SAS Version 9.3 to estimate missing observations. We will evaluate the degree of dependency between patients within a given group session, between patients in a given PACT, and between PACTs within each of the five sites (by examining Intra Class Coefficients). It is likely that significant dependency will exist, and if so, we will accordingly take these into account in analyses (i.e., patients will be nested within PACTs which will in turn be nested within sites). Random regression methods using SAS Proc Mixed will be employed to account for clustering of data.

5.6.C.i. H2 Analyses (Effectiveness) We will employ Analysis of Covariance (ANCOVA) to examine treatment differences in outcomes immediately post-intervention (at 4 months). We will conduct two models: one with HbA1c at post-intervention as the outcome and one with DDS at post-intervention as the outcome. Models will include treatment group (i.e., EPIC versus EUC) as a predictor and respective HbA1c and DDS baseline scores and any demographic,

clinical, or patient-centered variables that differed between the study arms at baseline as covariates. We will calculate treatment effect sizes immediately post-intervention.

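### Hypoglycemia, the risk the plan links to the intervention succeeding, is collected for oversight only; no EPIC versus EUC comparison of it is planned

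*Combined protocol and SAP*

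**What the plan says.** Section 5.1.J, on the risks of the intervention, states that "a small risk remains that some patients may experience hypoglycemia after successfully making these modifications". The eligibility text in section 5.2.B makes the same link: "Patients whose baseline levels fall below 7.5% may have limited ability for meaningful HbA1c change without significant concerns for hypoglycemia". Section 5.1.E.iii adds that EPIC one-on-one sessions come with standardized medication-management procedures and that the provider passes medication issues to the care team in a CPRS note. EUC patients have no such sessions (section 5.1.A).

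The effectiveness row of Table 5 reads "Intervention's impact on important outcomes, including negative effects like diabetes distress"; its measures are arm differences in HbA1c and DDS at 4 months, and the maintenance row repeats them at 10 months. For H2, section 5.6.C.i says "We will conduct two models: one with HbA1c at post-intervention as the outcome and one with DDS at post-intervention as the outcome", and 5.6.C.ii does the same at 10 months. The rest of 5.6.C covers costs and quality-adjusted life-years, implementation indices, growth curves and mediation. Table 10 lists no hypoglycemia measure.

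Hypoglycemia does appear in the oversight text. Section 5.1.N has adverse events presented at quarterly meetings and hypoglycemia-related hospitalizations reported to the Central IRB within five business days. Section 6.0 defines serious events by their relation to hypoglycemia and sends reports to a national DSMB. It lists three collection points: assessments, EPIC sessions and telephone contacts.

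For costing, section 5.5.A.i retrieves utilization data and describes one source thus: "The National Patient Care Database includes outpatient and inpatient clinical, demographic, and utilization data (e.g., patient age, race, diagnosis and procedure codes".

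**The concern.** The HbA1c models count a fall in HbA1c as benefit. Section 5.1.J says that the main physical harm may follow from the same success, and only EPIC includes the individual sessions in which medication issues are worked through. An arm difference in hypoglycemia is therefore plausible by design, and a reader weighing an HbA1c benefit would want to see it.

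Oversight reporting does not supply it. Reviewing individual events, or reporting them to an IRB, does not say whether they were more frequent under EPIC than under EUC. A comparison assembled later from the section 6.0 reports would be unsafe, because EPIC patients have a collection point that EUC patients lack.

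**Working it through.** **1. The plan's sample size.** Inputs from section 5.6.A: "All tests will be two-sided with an alpha of 0.05", d = 0.40, 80% power, ICC 0.0183, 12 patients per PACT, 15% attrition.
- n per arm at d = 0.40: 99 by calculation; the plan uses 100.
- Design effect: 1 + (12 - 1) x 0.0183 = 1.2013; 100 x 1.2013 = 120.
- Attrition: 120 / 0.85 = 141.2, rounded up to 142 per arm, 284 in total.

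The figure reproduces. It rests on HbA1c and DDS effect sizes alone; hypoglycemia plays no part in it.

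**2. Where a comparison could sit.**

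| Place | Content | Hypoglycemia by arm? |
|---|---|---|
| 5.1.I.b, primary outcomes | HbA1c, DDS | No |
| Table 10 | Measures by visit | No |
| Table 5 | HbA1c, DDS, reach, adoption, fidelity, cost | No |
| 5.6.C | HbA1c, DDS, cost, QALYs, growth curves, mediators | No |
| 5.1.N and 6.0 | Monitoring and reporting | No by-arm summary stated |

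**3. What 142 per arm could show.** The documents give no event rate, so all counts below are assumptions, and clustering is ignored.
- Zero events in an arm: upper bound 1 - 0.05^(1/142) = 2.1% (one-sided 95%); 1 - 0.025^(1/142) = 2.6% (97.5%).
- For non-zero counts, the Newcombe interval is built from the Wilson limits (l, u) of each arm: lower limit = D - sqrt[(p1 - l1)^2 + (u2 - p2)^2]; upper limit = D + sqrt[(u1 - p1)^2 + (p2 - l2)^2].

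| EPIC v EUC | EPIC % (Wilson) | EUC % (Wilson) | Difference, points (95% CI) |
|---|---|---|---|
| 7 v 3 | 4.9 (2.4 to 9.8) | 2.1 (0.7 to 6.0) | +2.8 (-1.8 to +7.9) |
| 14 v 7 | 9.9 (6.0 to 15.9) | 4.9 (2.4 to 9.8) | +4.9 (-1.3 to +11.4) |
| 7 v 1 | 4.9 (2.4 to 9.8) | 0.7 (0.1 to 3.9) | +4.2 (+0.2 to +9.2) |

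For 7 v 1, Fisher's exact test gives p = 0.066 although the Newcombe interval excludes zero. With counts this small the choice of method can change the reading, so one method should be named in advance.

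**4. Why not a test.** For a doubling of risk at 142 per arm, two-sided 0.05:

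| EUC v EPIC (assumed) | Power, normal approximation (Fisher) | n per arm for 80% |
|---|---|---|
| 2% v 4% | 17% (8%) | 1,141 |
| 5% v 10% | 36% (28%) | 435 |
| 10% v 20% | 66% (60%) | 199 |

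**5. Why not the section 6.0 reports.** Suppose an equal true risk of 20%, with 90% of events captured in EPIC and 50% in EUC. The observed risks are 0.20 x 0.90 = 18% and 0.20 x 0.50 = 10%, an apparent risk ratio of 1.8 where the truth is 1.0. The chance of a falsely significant difference is about 49%. At 70% capture in EUC it is about 15%. The capture rates are assumptions; the documents give none.

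**The case against.** **Safety is already covered.** Serious hypoglycemia-related events are documented, and events reach the IRB, the quarterly meetings and the DSMB. A reader might infer from the silence of 5.6.C that the harm goes unreported; the documents do not support that. What is absent is an arm comparison among the planned results. Section 5.1.N also refers to a data and safety monitoring plan that is not among the documents; it may contain by-arm tables for monitors, but that would not put a comparison into the results.

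**Table 5 is consistent.** It names distress as its example of a negative effect and measures distress through the DDS. This stands: the gap is an omission, not a contradiction within Table 5.

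**Hypoglycemia is not the only harm named.** Section 5.1.K also mentions symptoms of hyperglycemia. This too stands; hypoglycemia is singled out here because section 5.1.J ties it to the intervention's success.

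**The data are not in hand.** Section 5.5.A.i retrieves general utilization and cost data, and diagnosis codes are given only as an example of what one database holds. A reader might infer that hypoglycemia records are already being pulled for both arms; no text says so. They would have to be derived.

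**Coded encounters can also be uneven.** Up to six group and six individual sessions, with CPRS notes after the latter, give EPIC patients more chances to have mild episodes raised and coded in outpatient care. This is a sound objection, and the fix separates outpatient codes for that reason.

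**The risk is called small, and screening lowers it.** Patients whose clinicians advised against titration after significant hypoglycemic events are excluded, as are those with baseline HbA1c below 7.5%. The HbA1c and DDS inference is also untouched. All true, and it limits the weight of the point. But a low expected risk still has to be shown by arm.

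**Conclusion.** The concern holds as an omission. Hypoglycemia is collected for oversight, partly through contacts that only EPIC patients have, and no between-arm comparison is specified. The trial can report an HbA1c benefit without an unbiased arm-level statement of this harm. This warrants a low-cost addition to the analysis plan; it does not call the primary analyses into question.

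The size of any arm difference cannot be stated, because the documents give no rate. A descriptive table at 142 per arm would be informative but not tight: about 2.1% or 2.6% as the upper bound with zero events, and upper limits of 7.9 and 11.4 points in the 7 v 3 and 14 v 7 illustrations. These figures assume complete follow-up in the records and independent patients. It would be wrong to read them as showing that the trial could exclude an excess of about 5 points, or that a powered test is feasible for uncommon events.

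**What to change.** In section 5.6.C, with matching entries in the effectiveness and maintenance rows of Table 5, add a descriptive safety outcome to be shown beside the HbA1c result:
- **Population and period:** all randomized patients by assigned arm, from randomization to 10 months.
- **Main measure:** number and percentage with at least one emergency or inpatient encounter carrying a hypoglycemia diagnosis code, and events per person-year.
- **Comparison:** EPIC minus EUC risk difference with a 95% confidence interval by one pre-named small-sample method, such as the Newcombe score interval. No powered test.
- **Source:** the utilization data retrieved for costing under section 5.5.A.i, with one preset code list applied blind to arm.
- **Outpatient-coded events:** shown separately and labelled as open to greater ascertainment in EPIC because of its extra sessions and CPRS notes.
- **Not to be used for the comparison:** the safety reports collected under section 6.0.

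The cost is plan wording, one code list, one derivation from the costing extract and one table, with no new visits, staff or patients. The limitation is that coded encounters miss mild episodes and care outside the VA, so the result must be labelled as treated or recorded hypoglycemia. The change concerns analysis and reporting only and alters no clinical procedure.
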